**Table 9 Core safety evaluation and frequency**

Evaluation	Frequency
ECG	Baseline ECG prior to and 30 minutes after the first dose. Repeat ECG on 21 st day after injection for the first 3 months Repeat ECG every 3 months thereafter.
Gallstone assessment by CT/MRI is part of the evaluation	Baseline and every 6 months (done by ultrasound, at Mayo outside of baseline 12 and 36 months visits when MRI is performed)
Fasting glucose finger stick	Monitor FPG or finger stick at baseline and at 21 st day of treatment for the first 3 months.  Monitor FPG or finger stick monthly (or as clinically appropriate), thereafter. Monitor of FPG 4 weeks after the end of the treatment is recommended.
TSH/Free T4	Baseline and at 6 months
HbA1c*	Baseline and every 3 months Monitoring HbA 1c 3 months after the end of the treatment is recommended

### 7.1 Information to be collected on screening failures

Information on all screen failures will be collected and the analysis will be performed for all patients will be included who received at least one dose of the randomized study drug.

### 7.2 Patient demographics/other baseline characteristics

The ADPKD database at the Mayo Clinic includes 4577 patients. Approximately 500 patients with ADPKD or ADPLD are seen in the PKD Clinic, the Renal Transplant and Hepatobiliary Clinics every year. Mayo Clinic has the largest experience in combined hepatic resection/cyst fenestration for severe PLD. Ten percent of the patients undergoing renal transplantation at the Mayo Clinic in Rochester (~250 patients per year) have ADPKD. Pregnant women, children, prisoners, institutionalized individuals will not be randomized to this study. The proposed consent form is attached to this proposal.

### **7.3 Treatments**

All current medication used to treat diabetes mellitus should be documented

All medications, including over-the-counter medication, taken prior to study drug administration and which continue during the course of the study must be documented

Compliance will be assessed by the investigator and/or study personnel at each visit. Records of study medication used, treatment administered, and intervals between visits will be kept during the study. Drug accountability will be noted. Patients will be asked to return all used medication ampoules at each visit and the end of the study.

### **7.4 Efficacy**

#### **7.4.1 Liver & total kidney volume, hepatic cyst volume, renal cyst volume**

##### **7.4.1.1 Primary outcome**

The primary outcome is the percent change in liver volume as assessed by MR at baseline, 12 and 36 months follow-up. Patients will also be classified as “responders” if their liver volume decreases, does not change, or increases by <2% over the 12 month study period. The MR techniques for imaging and interpretation of volumetric measurements established in the CRISP study will be employed in the present study, as early results from the CRISP study indicate that this MR protocol will provide an effective means for longitudinal evaluation of liver and kidney volume and of cyst volume and is much more sensitive in detecting cholelithiasis when compared to CT, because CT cannot differentiate between the density of bile in the gallbladder and the more common, non-calcified gallstones. T-2 weighted images on MR can easily demonstrate stark contrast between the bright fluid (bile) in the gallbladder from the dark gallstones which do not have any signal intensity on MRI. The MR Procedure comprises of the following (30 minutes):

1. Since no gadolinium will be used in this study, patients will not have an angiocatheter placed at the time of their MRI. (See exception for patients undergoing CT below.)
2. ECG pads will be placed over the chest. If ECG gating is not available or functioning, it may be replaced with a peripheral pulse gating. Hair may need to be shaved off to place the leads.
3. Subjects will be placed supine on the MR table with their arms to their sides.
4. A phased-array surface coil will be positioned with its center over the liver.
5. Scout scan to locate the scan range of the entire liver.
6. The field-of-view (FOV) should be kept as small as possible (30-35 cm) without producing wrap-around artifacts.
7. Obtain breath-hold coronal Regular T2 scan (SSFSE/HASTE with fat sat) with 9mm fixed slice thickness, usually achievable in a single breath-hold.
8. Obtain breath-hold coronal Regular T2 scan (SSFSE/HASTE with fat sat) of the liver with adjusted slice thickness, 3-9 mm, i.e. the slice thickness best attainable with a single breath-hold (the adjusted slice thickness may not remain the same in a follow-up MR scan if there is a change in the subject's breath-hold capacity or liver size).
9. Repeat the scan over the kidneys with the same slice thickness.

The measurements of liver, kidney and cyst volumes will be performed without knowledge of group assignment using the technology developed for the CRISP study. Liver and kidney vol-

umes will be measured in T1-weighted images with a stereology method and calculated from the set of contiguous images by summing the products of the area measurements and slice thickness. A region-based threshold method will be used to calculate cyst volumes.

In patients who are unable to undergo MRI (e.g. due to claustrophobia) a CT scan of the liver and kidneys will be substituted. CT scans will be performed with or without contrast, depending of renal function. If estimated GFR is greater than 60 iodinated IV contrast will be employed. If renal function is less than 60mls/min, no iodinated contrast will be used. A peripheral IV cannula will be inserted for patients requiring IV contrast and removed immediately after the scan is completed.

#### **7.4.1.2 Secondary efficacy assessments**

Absolute and percent changes in liver volume in the placebo group before (year 1) and after (years 2-3) cross-over to active treatment will be assessed based on comparison of baseline volumes as assessed by MRI/CT in each subject. The measurements will be performed in the Biomedical imaging core facility by blinded assessors. Similarly, absolute and percent changes in liver volume will be assessed in the treatment arm during years 2-3 compared to the placebo arm during year 1. Similarly, changes in kidney volume from baseline at 12 and 36 months in individuals with ADPKD will be assessed by MRI.

Changes in eGFR, vital signs, creatinine, liver function tests, APTT, PT, glucose values from baseline (or from month 3) at 12 and 36 months in all individuals and treated as a continuous variable. Data from ADPLD patients will be excluded from the renal outcome sub-analyses.

Measurement of Effect (Subjective Response):

Changes in quality of life at baseline and 12 and 36 months will be measured by SF36-questionnaire QOL-questionnaire (SF-36v2™).

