#### **1.5.1.1 Pasireotide LAR**

A total of 85 patients were enrolled in the [CSOM230C2110] study and received at least one dose of pasireotide (SQ and/or LAR injection). Of these, 40 patients were diagnosed with acromegaly and 45 with carcinoid tumors. Patients received a single dose of 300 µg Pasireotide SQ followed by a washout period of at least 5 days. Patients subsequently received 3 monthly administration of pasireotide LAR IM.

In patients with acromegaly, the most common AE overall and by treatment group was diarrhea affecting 12/35 patients in total, 3/10, 3/12 and 6/13 in the pasireotide LAR 20 mg, 40 mg and 60 mg group, respectively. Majority of the diarrhea were CTCAE grade 1 and none were serious. Frequent AEs only reported in the 40 mg and 60 mg groups included abdominal distension, cholelithiasis, blood glucose increased, hyperglycemia and hematuria. All events but blood glucose increased in the 40 mg group (2 patients) and hyperglycemia in the 60 mg group (3 patients) were observed for one patient in each of the two groups.

In patients with carcinoid tumors, diarrhea was the most frequent AE affecting 4 patients in each treatment group (4/12 in the 20 mg group, 4/14 in the 40 mg group, and 4/16 in the 60 mg group). Diarrhea side-effects were of CTCAE grade 1 or 2 for all patients, except for one patient in the pasireotide LAR 20 mg group, for which the AE was reported as grade 3. Other frequently reported AEs were fatigue (9/42 patients), asthenia (5/42 patients), diabetes mellitus (6/42 patients), anorexia (5/42 patients), back pain (4/42 patients) and muscle spasms (3/42 patients). CTCAE grade 3 or 4 that were suspected to pasireotide LAR were primary hyperglycemia and

were reported in all dose groups. CTCAE grades 3/4 elevation of blood glucose level was reported in 18/42 (43%) patients. Median time to grades 3/4 elevation of blood glucose occurred on day 1 of cycle 1 (range 1-1131 days), approximately 6 hours (range 2-8 hours) post-dose.

Given the observed suppression of insulin secretion associated with pasireotide administration, the use of insulin secretagogues and/or incretin-based therapies may be particularly suited for the treatment of pasireotide induced glucose dysregulation.

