#### **1.5.1.1.1 Clinical pharmacokinetics**

Pasireotide SQ and LAR have been studied in healthy volunteers, patients with acromegaly, Cushing's disease and carcinoid syndrome. Following a single IM injection of 40 mg or 60 mg in healthy volunteers [CSOM230C2101], pasireotide LAR demonstrated a controlled release type of concentration-versus-time profile, with an initial spike phase on day 1 followed by a slow-release process for up to 42 days. The Cmax of the extended release phase was observed approximately on day 20 for both dose levels. Pasireotide LAR was also investigated in patients with acromegaly and carcinoid tumors [CSOM230C2110]. Following monthly (q28 days) IM injections of 20, 40, or 60 mg pasireotide LAR, preliminary results showed an approximately linear dose-exposure proportionality and a steady state achieved following 3 injections. The PK exposure to pasireotide at steady state in acromegalic patients was comparable to the simulated PK exposure at steady state in healthy volunteers, whereas, the PK exposure in patients with carcinoid tumors was roughly 2-fold that in acromegalic patients.

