For studies with ongoing enrollment using the LAR formulation: Liver function tests (LFTs) must be assessed at screening, baseline, Day 22 after the first injection, Day 29, Day 50, Day 57 and Day 85. After Day 85, monitoring should follow the existing protocol schedule. The Day 22 and Day 50 LFTs must be available and assessed prior to dosing on Day 29 (2nd injection) and Day 57 (3rd LAR injection). For studies with ongoing enrollment using s.c. or LAR formulation: Revised exclusion criteria for LFTs (**Table 1**).

For all ongoing studies: Additional hepatic management (i.e. liver-directed history and physical examination, LFTs, hepatitis screen, abdominal ultrasound, and PK sample) is to be implemented within 72 hours of awareness of abnormal liver function tests. Follow-up LFT monitoring will take place at 3-4 day intervals for all s.c. and LAR studies (**Table 2**).

For all ongoing studies: Additional LFT discontinuation criteria are to be implemented (**Table 7**).

An algorithm of LFT management for all SOM230 s.c. and LAR studies is provided in appendix 4.

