### **3.2 Secondary objectives**

Absolute and percent changes in liver volume in the placebo group before (year 1) and after (years 2-3) cross-over to active treatment

Absolute and percent changes in liver volume in the treatment arm during years 2-3 compared to the placebo arm during year 1

Changes in eGFR from baseline (or from month 3) at 12 and 36 months in individuals with ADPKD

Changes in kidney volume from baseline at 12 and 36 months in individuals with ADPKD

Symptoms at baseline, 12 and 36 months. Changes in symptoms, measured by SF36-questionnaire QOL-questionnaire

Quality of Life at baseline, 12 and 36 months. Changes in quality of life, measured by SF36-questionnaire (SF-36v2™)

Responders at 12 and 36 months.

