#### 6.2 Treatment arms

There will be stratified randomization for PLD patients with ADPLD and ADPKD (see Table 5):

All participants who receive the placebo during year one will be given the option to continue on study to receive active study drug for years two and three. Thus, all participants will be receiving SOM230 years two and three.

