### 10.2 Statistical methods

Demographics and laboratory data will be plotted (e.g. box plots) and summarized by treatment group. Frequency distributions will be used to describe categorical values and basic summary statistics (mean, standard deviation, median, and inter-quartile range) used to describe continuous values. All tests will be two-sided with alpha level 0.05. For quantitative endpoints (e.g. change in kidney and liver volumes, renal function, and SF-36 scales) the two-group independent samples t-test will be used to test for an effect of treatment. Should the assumptions of normality and equality of variances be untenable, we will consider a data transformation or use of the Wilcoxon rank sum test. Both point estimates (mean) and 95% confidence intervals will be used to summarize treatment effects. For qualitative endpoints (e.g. presence or absence of response) we will compare treatment groups using the chi-square or Fisher's exact test as appropriate.

**Efficacy (Liver & kidney):** The primary analysis of treatment efficacy will follow intent-to-treat principles, attempting to include all randomized patients. For the primary endpoint (change in

liver volume) we will not be able to include anyone without a 12 month MRI (kidney volumes will be handled in the same way). For the “response” endpoints, those without a 12 month MRI will be included in the analysis as non-responders. Secondary analysis – Efficacy (QOL): We will have up to 5 longitudinal assessments of QOL for each patient. Repeated measures analysis of variance will be used to compare mean QOL profiles over time between treatment groups. Also, within patient rates of change or slopes in QOL measures will be estimated (using simple linear regression) and compared between groups using the two-sample t-test.

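### Section 7.4.1.2 lets glucose, liver-test and other laboratory change be counted from month 3, an on-treatment value in the SOM230 arm; the objectives allow that origin for eGFR only

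*Combined protocol and SAP*

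**What the plan says.** All references are to the combined protocol and SAP.

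- **Section 7.4.1.2** covers eGFR, vital signs, creatinine, liver function tests, APTT, PT and glucose in a single sentence, which ends "glucose values from baseline (or from month 3) at 12 and 36 months in all individuals and treated as a continuous variable". It does not say which origin belongs to which measure, which is the main one, or who decides.
- **Section 3.2** has the month-3 option in one line only: "Changes in eGFR from baseline (or from month 3) at 12 and 36 months in individuals with ADPKD". Kidney volume is taken from baseline. Glucose and liver tests are not among the secondary objectives.
- **Dosing** is every 28 days (section 2.1). The liver-test schedule in section 1.5.2 requires results to be in hand "prior to dosing on Day 29 (2nd injection) and Day 57 (3rd LAR injection". Table 8, footnote 4, links day 85 with the fourth injection.
- **Section 1.5.1.1.1** reports, from preliminary data in acromegaly and carcinoid patients, "a steady state achieved following 3 injections".
- **Section 10.2** says of laboratory data: "Demographics and laboratory data will be plotted (e.g. box plots) and summarized by treatment group". Its general rule for quantitative endpoints is that "the two-group independent samples t-test will be used to test for an effect of treatment".
- **Section 8** compares year-1 adverse events between the arms with Fisher's exact test.

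**The concern.** A change score needs an origin that treatment has not touched. Baseline meets that condition in both arms. Month 3 meets it only in the placebo arm, because SOM230 patients have by then been injected three times. If month 3 is used, the month-12 contrast measures only what happened between months 3 and 12, and any drug effect that arose earlier is removed.

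Month 12 is the only time point listed in 7.4.1.2 at which a placebo arm is still running alongside; after that, "Thus, all participants will be receiving SOM230 years two and three". An early and lasting shift in glucose or liver tests could then appear as little or no difference from placebo in the one randomised comparison available. Because the plan leaves the origin open, the choice could also be made after the data are seen.

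**Working it through.** **1. Scope of the option.** Section 3.2 attaches it to eGFR in ADPKD patients. Section 7.4.1.2 attaches it to seven kinds of measure in all individuals. The phrase does not fit that longer list: Table 8, so far as its extracted layout can be read, shows no PT/APTT sample between screening and month 6, so there would be no month-3 value to start from. This suggests that the phrase was carried over from the eGFR line, but as written it governs the whole list.

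**2. Injections before month 3.** Nominal injection days are 1 + 28k: 1, 29, 57, 85. A pre-dose sample on day 85 follows three injections. No visit is labelled month 3, and section 4 writes day 89 where Table 8 has day 85; a day-89 sample nominally follows four. With every interval at 30 days (injections on days 1, 31, 61, 91), three precede day 89. With every interval at 26 days (days 1, 27, 53, 79), four precede day 85. Under any of these readings the SOM230 value is on treatment.

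**3. What the origin does to the estimate.** Let e3 and e12 be the mean SOM230-minus-placebo effects at months 3 and 12, with equal expected baselines by randomisation.

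- Contrast from baseline at month 12: e12.
- Contrast from month 3 at month 12: e12 − e3.
- Share lost: f = e3 / e12.

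If f = 0 there is no loss; if f = 1 the whole difference disappears. The documents give no value of f for these patients.

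**4. Illustration of size.** This step applies only if the t-test in section 10.2 is used for these measures. Inputs are 15 placebo and 30 SOM230 patients and two-sided alpha 0.05 (section 10.2), giving 43 degrees of freedom. For a difference of d SD the noncentrality is d / √(1/15 + 1/30) = 3.16d. The plan says that the study can detect at least 1 SD for any quantitative endpoint; d = 1 gives 87% power, and 80% is reached at 0.91 SD, so that statement is reproduced. Now assume a true month-12 effect of 1 SD, and let the SD of change from month 3 be the same, 20% smaller or 30% smaller than that from baseline:

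| Origin and share present at month 3 | Expected difference | Power, same SD | SD 20% smaller | SD 30% smaller |
|---|---|---|---|---|
| Baseline, any share | 1.00 SD | 87% | – | – |
| Month 3, 25% | 0.75 SD | 64% | 83% | 91% |
| Month 3, 50% | 0.50 SD | 34% | 49% | 60% |
| Month 3, 75% | 0.25 SD | 12% | 16% | 20% |
| Month 3, 100% | 0 | 5% | 5% | 5% |

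Differences are in units of the SD of change from baseline. Power is not always lost: with 25% present and a 30% smaller SD it is 91% against 87%. The estimate is still short by the share f. Effect size, share and SD ratio are all assumed.

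**5. Month 36.** If the arms were compared from month 3 and had the same on-drug effect e36, the SOM230-first arm would show e36 − e3 and the placebo-first arm e36, a difference of −e3 produced by unlike origins. No section prescribes this comparison for these measures, so it is a reason to avoid the month-3 origin, not a predicted error.

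**The case against.** Several points on the other side are sound.

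- **Baseline is named first.** Month 3 is an alternative in brackets. A reader might infer that the plan will use it for glucose and liver tests; the text says only that it may.
- **An early, lasting effect is not shown.** A reader might infer one from section 1.5.1.1: "Median time to grades 3/4 elevation of blood glucose occurred on day 1 of cycle 1". The same sentence places this about 6 hours after the dose, with a range of 1 to 1131 days, in carcinoid patients. Such a peak does not establish a shift in fasting glucose at day 85, and section 7.5.4 requires fasting samples. Section 1.5.2.1 reports that glucose rises in healthy volunteers generally resolved within 3 to 4 weeks of an injection, and that the few liver or pancreatic enzyme rises also resolved. Steady exposure after three injections is not proof of a steady effect.
- **No test is named for these measures.** The examples in section 10.2 are organ volumes, renal function and SF-36 scales. A reader might infer a definite loss of power; if these measures are only summarised, there is no test to lose power.
- **Other safeguards exist.** Rises that are treated or considered clinically significant count as adverse events (section 7.5.1) and enter the year-1 comparison. Dose rules and the six-monthly safety committee do not depend on the change score. A reader might infer that early hyperglycaemia would go unseen; it would not.
- **HbA1c is not neglected.** It is collected every 3 months and falls under the by-arm laboratory summaries. Its absence from the 7.4.1.2 list is not an error.

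These points limit the consequence. They do not remove the mismatch between 3.2 and 7.4.1.2, nor make day 85 an untreated value.

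**Conclusion.** The point holds in a limited form. Section 7.4.1.2 permits an on-treatment origin for glucose, liver tests, vital signs, creatinine and PT/APTT that the objectives reserve for eGFR. If that origin is used, the month-12 difference from placebo is reduced by whatever effect is present at month 3. The amount is unknown: none if no effect is present by then, all of it if the effect is complete by then. That the month-3 value is on treatment rests on the injection schedule alone; that harm follows rests on the further, unproven assumption that some effect is present at that visit.

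The power figures are illustrations, and the documents do not support a false-positive claim at month 36. The matter concerns secondary and safety measures, not the primary liver-volume endpoint. It is worth correcting because the present wording allows a biased contrast and the correction is almost free.

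**What to change.** In section 7.4.1.2:

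- make baseline the only origin for glucose, liver tests, vital signs, creatinine, PT/APTT and any other non-eGFR measure;
- keep the month-3 option for eGFR alone, as in section 3.2, and state which eGFR origin is the main one.

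The cost is a few words, with no new samples or visits. Adding HbA1c change from baseline to the list is an optional extra that uses values already collected. I would not ask for worst-value glucose tables: Appendix 2 says that finger-stick diary values need not be entered in the database, so such tables could miss values or require new data entry.

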#### **7.4.1.3 Tertiary objectives**

We will assess longitudinal changes beyond 12 months in the above factors, stratified by treatment sequence.

### **7.4.2 Treatment/Follow-up Decisions at Patient Evaluations**

Response to treatment will be analyzed by measuring changes in liver volume. The study is intended to provide information after 12 months of treatment. Follow-up decisions will proceed as follows: if the treatment is found to be definitively or possibly effective (reduction in liver volume, no increase or increase < 2% per year), all participants treated with will be offered Pasireotide LAR® Depot treatment for another 24 months. The participants treated with placebo will also be offered at this point treatment with Pasireotide LAR® Depot for 24 months.

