**Secondary analysis–Kidney volume will be measured as part of the efficacy analysis:**

AEs (both patient and event counts) will be tabulated by organ system (neuro, GI, etc.), individually, by severity and, for each severity, by investigator-assessed relationship to study drug. Fisher’s exact test will be used to compare treatment groups regarding adverse events. Patients who received at least one dose of the randomized study drug will be included.

**Statistical power:** The primary endpoint is one year percentage change in liver volume. Prior data in untreated patients suggest a growth rate (SD) of 5(±3) % per year. We have planned a 2:1 randomization in order to allow as many patients as possible to receive SOM230. The goal is to detect up to a 7.3% percentage point decrease in the mean cyst growth using SOM230 LAR® Depot. With **15 placebo and 30 SOM230** patients, the study will have 80% power (alpha=.05, two-sided) to detect a 7 percentage point difference. To allow for dropouts (1 placebo and 2 SOM230 patients without endpoint data); the study will randomize 16 placebo and 32 SOM230 patients. For any quantitative endpoint the study is powered to detect a difference in treatment means of at least one standard deviation. Secondary endpoints include comparison of responder rates (based on liver and renal growth) and adverse event rates between the two groups. With 16 and 32 patients, a true placebo response (or adverse event rate) of 8 % (1 of 13) vs. 30, 40, or 50% for SOM230 can be detected with 45%, 70%, and 88% power, respectively.

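### The year-1 effectiveness bar in section 7.4.2 has no placebo contrast, and the 8% placebo rate behind the responder power does not match the plan's other inputs

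*Combined protocol and SAP*

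**What the plan says.** **Year-1 decision.** Section 7.4.2 makes the offer of a further 24 months of SOM230 "if the treatment is found to be definitively or possibly effective (reduction in liver volume, no increase or increase < 2% per year"). No comparator, test or interval is given, the two grades of effectiveness are not separated, and the unit judged (patient or arm) is not stated. Section 6.10 says the open-label extension will be terminated if the first-year analysis finds no efficacy, without saying what efficacy is. Section 6.2 describes active drug in years 2 and 3 for all participants, with no condition attached.

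**Responder endpoint.** Section 7.4.1.1 classes a patient as a responder if "liver volume decreases, does not change, or increases by <2% over the 12 month study period". For missing scans, section 10.2 says that "those without a 12 month MRI will be included in the analysis as non-responders". The power paragraph of section 10.2 widens the basis: "Secondary endpoints include comparison of responder rates (based on liver and renal growth"), with no renal cut-off given. It then takes "a true placebo response (or adverse event rate) of 8 % (1 of 13) vs. 30, 40, or 50% for SOM230" with 16 and 32 patients and prints power of 45%, 70% and 88%. No source is cited for the 8%. The test is left open: "For qualitative endpoints (e.g. presence or absence of response) we will compare treatment groups using the chi-square or" Fisher's exact test, as appropriate.

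**Growth figures.** The power paragraph states: "Prior data in untreated patients suggest a growth rate (SD) of 5(±3) % per year". Section 1.5.2.2 reports the earlier octreotide trial's placebo arm (n = 14) as 0.92 ± 7.00%, and later as net growth of 0.9 ± 8.35%.

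**The concern.** A bar of less than 2% growth, with nothing to compare it to, cannot separate a drug effect from slow natural growth. The earlier trial's placebo arm, reported as growing about 0.9%, would itself have met it. Section 7.4.2 is also the only place where the plan says what effective means for the year-1 decision.

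The 8% placebo response should follow from the responder cut-off and the assumed growth, and it does not. The number 13 cannot be traced either: the earlier trial had 14 placebo patients, and this one plans 15 evaluable and 16 randomized. At stake are the wording of the year-1 conclusion and how informative a secondary endpoint can be expected to be.

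**Working it through.** **Assumption.** Percent change in liver volume is taken as normal, which the documents do not state. The earlier placebo change is taken as growth, as sections 1.3 and 1.5.2.2 call it. Section 1.5.2.2 also shows the mean volume going from 5374 to 5361 ml, so the sign is not clear. If it was a decrease, an inert drug would pass more often.

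**1. The plan's own power figure.** Use the normal two-proportion formula with n = 2/(1/16 + 1/32) = 21.33 per arm and p̄ = (p1 + p2)/2:

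z = [(p2 − p1)√n − 1.96√(2p̄(1 − p̄))] / √(p1(1 − p1) + p2(1 − p2))

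With p1 = 0.08 and p2 = 0.30, z = (1.016 − 1.087)/0.533 = −0.134, so power is 44.7%. For 40% and 50% it is 70.0% and 88.5%. The printed 45/70/88% is therefore reproduced. Pooling weighted by arm size gives 38/67/88% instead.

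**2. The 7.4.2 bar, inert drug, arm mean of 30.** P(pass) = Φ((2 − m)/(s/√30)):
- 0.92 ± 7.00: Φ(0.845) = 80%
- 0.9 ± 8.35: Φ(0.722) = 76%
- 5 ± 3: Φ(−5.48), below 0.1%

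The earlier mean comes from 14 patients (95% CI −3.1 to 5.0%, or −3.9 to 5.7%). Replacing s/√30 by s√(1/30 + 1/14) gives 68% and 66%. Read per patient instead, 16% to 56% of untreated patients would count as effectively treated (step 3).

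**3. Placebo responder rate implied by the <2% cut-off.** P = Φ((2 − m)/s), then times 15/16 because the plan allows for dropouts ("To allow for dropouts (1 placebo and 2 SOM230 patients without endpoint data")) and counts them as non-responders:
- 5 ± 3: Φ(−1) = 15.9%; with the dropout 14.9%
- 0.92 ± 7.00: 56.1%; with the dropout 52.6%
- 0.9 ± 8.35: 55.2%; with the dropout 51.8%

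If 5 and 3 are rounded values (4.5-5.5 and 2.5-3.5), the first figure ranges from 8% to 24%.

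**4. SOM230 responder rates on the same footing**, times 30/32 for two dropouts:
- 5 ± 3 less 7 points (−2 ± 3): 90.9%, then 85.2%
- earlier octreotide arm (−4.95 ± 7.00): 84.0%, then 78.7%
- earlier pooled octreotide data (−6.08 ± 7.58): 85.7%, then 80.3%

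**5. Exact power at 16/32**, by full enumeration of the binomial tables, two-sided 0.05, uncorrected chi-square and Fisher:

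| Placebo rate vs SOM230 rate | Chi-square | Fisher |
|---|---|---|
| 8% vs 30/40/50% | 40/70/90% | 35/62/84% |
| 16% vs 30/40/50% | 16/40/67% | 13/31/57% |
| 15% vs 30/40/50% | 18/44/71% | 15/34/60% |
| 15% vs 85% (plan's 5±3%, 7-point effect) | near 100% | near 100% |
| 53% vs 79% (earlier trial) | 48% | 38% |
| 52% vs 80% (earlier trial, pooled) | 56% | 46% |

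At a placebo rate of 52-56%, all three of the plan's SOM230 rates lie below placebo.

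**The case against.** The placebo comparison is in the plan. Section 3.1 sets the primary objective against the placebo arm, and section 10.2 tests it with a two-group test. Section 6.10 can fairly be read as meaning that analysis when it speaks of efficacy. Section 7.4.2 governs who is offered open-label drug, and no inference in section 10.2 uses its bar. A reader might infer that the trial could declare efficacy without a control; the documents do not support that. What stands is that section 7.4.2 uses the language of effectiveness with its own uncontrolled criterion, and that sections 6.2, 6.10 and 7.4.2 do not say the same thing.

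On the 8%, the sentence serves response and adverse events alike and may be only an illustration of detectability. One or fewer responders in 13 has probability 0.36 when the true rate is 16%, so that count does not contradict 16%. The rounding range touches 8% at its extreme corner (mean 5.5, SD 2.5). A definition requiring renal response as well could lower the placebo rate, but none is written down. All this stands, and it limits the point to an uncited input that does not match the plan's central figures.

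A reader might also infer that responder power is overstated. That follows only if the placebo rate is changed and the SOM230 rates stay at 30/40/50%. With both arms taken from the plan's 5±3% and 7-point effect, power is near 100%.

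**Conclusion.** The point holds with limits, and is minor to moderate. The 7.4.2 bar can label an inert drug effective: 76-80% of the time (66-68% with sampling error) on the earlier trial's placebo growth, and almost never under 5±3%. These figures rest on an arm-mean reading, normality and a 14-patient placebo arm. The width of the range shows that the bar's meaning depends on a placebo growth rate on which the plan's own sources disagree.

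The 8% placebo response does not match the roughly 16% (15% with the planned dropout) implied by 5±3%, or the 52-56% implied by the earlier placebo data. The printed power is correct arithmetic for the normal formula, so it should not be called a miscalculation. Even at 8%, however, exact power against 30% is 35-40%, not 45%. The direction of the error is not fixed: it depends on the SOM230 rate assumed alongside. The primary test and the sample size use neither the 8% nor the <2% bar and do not change.

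**What to change.** - Rest any year-1 conclusion that SOM230 is effective on the month-12 between-arm comparison in section 10.2, not on the <2% bar alone.
- Reconcile sections 6.2, 6.10 and 7.4.2 on what counts as efficacy for the extension and whether it is judged per patient or per arm. The rule itself is for the sponsor to set.
- Use one responder definition in sections 7.4.1.1 and 10.2: liver only, or liver and renal with a stated renal cut-off.
- Give the source of the 8%, and restate the responder power with placebo and SOM230 rates derived from the same growth assumptions, over placebo rates from 8% to about 55%. Name the test and count missing month-12 MRIs as non-responders.

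The cost is wording and one recalculated secondary-endpoint figure, which may look less favourable. No extra patients or data are needed.
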